9.0 Procedures Involved*

9.1 Our study is a double-blind randomized placebo-controlled trial.

- Treatment arm: Injection of 300 units of abobotulinum toxin A in 10 ml of non-bacteriostatic normal saline to chosen hand.
- Control arm: Injection of 10 ml of non-bacteriostatic normal saline to chosen hand.
- Randomization will be determined by coin flip as follows:
 - Heads: Right hand – treatment arm; Left hand – control arm.
 - Tails: Right hand – control arm; Left hand – treatment arm.

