- All solutions will be prepared and drawn up by [name] the day of use after consent has been obtained and discarded immediately after use.
- The syringes will be labeled with a red or blue label for randomization by [name], [name], or [name].
- Screening and consent:
 - Each participant will sit down with the principal investigator to discuss the study in depth and review the screening criteria. After all risks, benefits, alternatives, and questions have been discussed consent will be obtained.
 - After the informed consent form is signed, the eligibility screening portion of the case report form will be filled out by the principal investigator with the research subject. If necessary, a pregnancy test will be performed.
- Administration of study solution:
 - 10 sites on each palm will be used (see image below):
 - a. Two at the base of the thumb
 - b. Three in the middle of the palm
 - c. Five at the proximal base between each finger

PROTOCOL TITLE: The Effect of Abobotulinum Toxin A on the Symptoms of Raynaud's Phenomenon, a Double-Blind Randomized Placebo-Controlled Trial

- The participants' sites of administration will be cleansed with isopropyl alcohol before administration. Needles will be introduced at a 90-degree angle subcutaneously. 1 ml of solution will be injected per site.
- A board-certified dermatologist, [name], will be administering all solutions to minimize risks for participants.
- Subjects will be given the clinic number and asked to call if they think they are experiencing any adverse effects.
- Subjects will be evaluated either in person or over the phone 1 month and 3 months after treatment.
- Disposal protocol:
 - After use, needles will be disposed of in red sharps container according to UCF Health policy.
 - After use, urine samples will be disposed of in the toilet according to UCF Health policy.

9.3

- Risk Management:
 - Participants will be directly observed during the administration of the botulinum toxin and placebo for any adverse events. An anaphylaxis kit is available in clinic should any participant experience such an event. The principal investigator is certified in basic cardiopulmonary life support and an AED is present in the facility. Participants will be provided with the phone number of the

PROTOCOL TITLE: The Effect of Abobotulinum Toxin A on the Symptoms of Raynaud's Phenomenon, a Double-Blind Randomized Placebo-Controlled Trial

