12.0 Provisions to Monitor the Data to Ensure the Safety of Subjects*

12.1 The plan to periodically evaluate the data collected regarding both harms and benefits to determine whether subjects remain safe is as follows:

- The principal investigator and statistician will review cumulative VAS Pain scores, RCS data, QuickDASH, number of digital ulcers, and number of attacks/episodes per week data at the halfway point (8 subjects).
- If any of the change in VAS Pain scores, RCS, QuickDASH, number of digital ulcers, or number of attacks/episodes per week for the treatment should become statistically significantly worse than the control with a $p < 0.05$ then the study will be suspended immediately.
- Alternatively, if the change in VAS Pain scores, RCS, QuickDASH, number of digital ulcers and number of attacks/episodes per week for the treatment should become statistically significantly better than the control with a $p < 0.05$ then the study will also be suspended immediately.

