24.0 Provisions to Protect the Privacy Interests of Subjects

24.1 Subjects will be in the same general vicinity during study and will be recruited from UCF Health Clinic. Therefore, there will be the possibility that participants may know and recognize each other.

24.2 Prior to enrollment subjects will be made aware of this possibility and if unacceptable, will be given the option to decline to participate.

24.3 All investigators will have access to all of the information collected on the subjects. The "Subject ID Assignment Log" will be kept in a separate folder so that investigators will only have access to identifiable information if needed for data entry or if there is a data discrepancy. Only de-identified data will be exported and used for data analysis.

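### The toxin hand is set by an unlogged coin flip and the syringes carry red or blue labels not tied to it, so the stated procedure does not secure the double blind, and treated side is left to chance.

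*Combined protocol and SAP*

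**What the plan says.** Section 9.1 claims a double blind ("Our study is a double-blind randomized placebo-controlled trial") and gives each patient toxin in one hand and saline in the other. On allocation it says "Randomization will be determined by coin flip as follows", and the rule is explicit: "Heads: Right hand – treatment arm; Left hand – control arm", with tails the reverse.

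Section 9.2 (Solution preparation) has the solutions drawn up "the day of use after consent has been obtained and discarded immediately after use" and adds a second device: "The syringes will be labeled with a red or blue label for randomization". The protocol does not say what each colour means, whether the code is fixed or changes by subject, who holds it, who flips the coin, or where the result is written down.

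Section 9.3 lists ten source documents. One is a Drug Accountability Log; none is a randomization or allocation log.

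On access, section 24.3 states "All investigators will have access to all of the information collected on the subjects". Its only limit concerns identity: "investigators will only have access to identifiable information if needed for data entry or if there is a data discrepancy". Section 11.3 keeps the paper forms, including the Drug Accountability Log, in a locked drawer with restricted access. At 8 subjects, section 12.1 provides that "The principal investigator and statistician will review cumulative VAS Pain scores, RCS data" and the other outcomes, comparing treatment with control. It does not mention masking the arms.

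**The concern.** RCS, VAS Pain, QuickDASH and attack counts are subjective. Each patient is also their own comparator, so a rater or patient who knows the toxin hand can move the two hands' scores in opposite directions. Blinding therefore carries much of the trial's credibility, and it has to rest on a procedure as well as on the title.

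Here the allocation event itself discloses the arm, the coding step is not connected to it, and no listed record would show that a flip was repeated or wrongly applied. Separately, an unrestricted flip in a trial of 16 can leave toxin mostly on one side. If right and left hands differ for other reasons, such as dominance, that difference enters the estimate. Hand dominance is not in the data list of section 9.4, so it could not be adjusted for.

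**Working it through.** **Plan's own figure.** Section 11.2 gives a 2-point RCS difference, SD 1.92, power 0.8 and alpha 0.05; section 11.1 gives two-sided independent-samples t-tests. d = 2/1.92 = 1.04. The noncentral-t calculation gives 15.53, so 16 per arm, with power 0.812. Each patient supplies one hand to each arm, so 16 patients reproduces. The point below does not change this number.

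**Blinding: what the labels can mean.** The text allows three readings.

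1. *Colour marks the solution, with a fixed code.* The injector must be told which colour goes to which hand, which by itself reveals nothing. But once one patient's toxin hand becomes evident, the code is known, and anyone who knows the other patients' colour-to-hand assignments can decode them. Such an event is foreseeable: section 14.1 lists temporary muscle weakness lasting up to 6 weeks, and the 1-month visit (+/- 8 days) falls inside that period.
2. *Colour marks the solution, with a code that varies by subject.* One unblinding then stays with one patient. But a key must exist for each subject, and no listed document holds it.
3. *Colour marks the hand.* The labels then disclose nothing, and the blind depends wholly on who sees the flip and who fills the syringes.

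Under all three, anyone who sees the flip and knows the heads/tails rule is unblinded for that subject.

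**Access.** Section 24.3 opens all collected information to all investigators. Section 11.3 restricts the drawer that holds the Drug Accountability Log, on which section 29.1 records administration. Neither section mentions allocation, and they cannot both apply to that log without qualification.

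**Side balance.** Assume a fair coin, with k of n = 16 patients receiving toxin on the right, k ~ Binomial(16, 0.5).

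| Split | Probability |
|---|---|
| exactly 8:8 | 12870/65536 = 0.196 |
| 10:6 or worse | 0.455 |
| 11:5 or worse | 0.210 |
| 12:4 or worse | 0.077 |

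If right and left hands differ by s points regardless of treatment, the mean toxin-minus-saline difference is shifted by s(2k/n − 1).

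- 11:5: 0.375s. 12:4: (24/16 − 1)s = 0.5s.
- The documents give no value for s. Assuming s = 0.5 to 1 RCS point, a 12:4 split shifts the effect by 0.25 to 0.5 point, or 12.5% to 25% of the 2-point target.
- Expected shift: zero. Mean absolute shift: 0.196s, or about 0.10 to 0.20 point over the same range.
- Standard error of the planned contrast: 1.92 × √(2/16) = 0.68 point.

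At the 8-subject review, 4:4 has probability 0.273 and 6:2 or worse 0.289; a 6:2 split also shifts by 0.5s.

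**The case against.** A reader might infer more than the documents support.

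- *That the flip is open.* The text does not say who flips or who sees it. Staff names are removed from the public version, so overlap between preparer, labeller, injector and assessor cannot be judged.
- *That patients can be steered into an arm.* They cannot: every subject receives both treatments, a fair flip is unpredictable, and solutions are drawn up after consent. What remains is a repeated, misapplied or knowingly chosen hand.
- *That no record of allocation exists.* The list shows no dedicated log, but the Drug Accountability Log and case report forms are attachments outside the text and may record treated hand or colour.
- *That section 24.3 discloses allocation.* It is a privacy section that does not mention allocation, and section 11.3 points the other way.
- *That one unblinding reveals all 16.* This needs a fixed colour code, which is not stated.
- *That the arms are unbalanced.* They are always 16:16; only side is left to chance, without bias on average. Even the 0.5-point shift is below one standard error.

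It can also be said that equal 10 ml volumes at the same ten sites protect the blind, that investigators' access to data does not in itself unblind a patient completing a survey, and that a blocked list is more predictable than independent flips. The first two are fair and limit the concern. The third is met by keeping block sizes undisclosed; since each patient receives both treatments, predictability could not be used to select patients into an arm.

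None of this supplies the missing link between flip and colour, the allocation log, or a rule on who may see the allocation.

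**Conclusion.** The point stands as a weakness in the stated allocation and coding procedure. It does not show that blinding has failed or that the estimate is biased. The flip names the hand, the colours are not tied to it, no allocation log is listed, and the access statements conflict. For subjective within-patient outcomes, that is too little to secure the double blind. The size of any unblinding bias cannot be calculated from the documents.

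Side imbalance is secondary. An exact 8:8 split is expected in about one trial in five, and 12:4 or worse in about one in thirteen. The resulting shift of 0.25 to 0.5 RCS point rests on an assumed right-left difference of 0.5 to 1 point. The case for change is that a better method costs very little.

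**What to change.** - **Allocation (9.1).** Replace the coin flip with a computer-generated list made before the first patient, blocked on toxin side with block sizes not disclosed. Assign entries in sequence only after eligibility is confirmed, so that balance holds among treated subjects and not just among the 20 enrolled. Fixed blocks of 4 give 8:8 at 16 subjects; random blocks of 2 and 4 give at worst 9:7.
- **Custody (9.2, 9.3).** Have the syringe preparer hold the list, keep that person out of injection and assessment, and add a restricted allocation log to the source documents.
- **Labels (9.2).** Replace red/blue with subject number plus RIGHT or LEFT.
- **Access (24.3, 11.3, 12.1).** State that allocation records are withheld from the injector and assessors until database lock, and align sections 24.3 and 11.3. Reconcile this with the 8-subject review: for example, the statistician runs the comparison and the principal investigator sees masked hands.
- **Optional (9.4).** Record hand dominance.

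The cost is about an hour of statistician time (an estimate) and new labels. The planned 16 patients are unchanged. The real constraint is keeping the preparer separate from injection and assessment; whether present staffing allows this cannot be confirmed from the public text.

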9.4 Data to be collected

- Age
- Gender
- Race
- Ethnicity
- Medical History
 - Past Medical and Surgical History
 - Medications
 - Allergies
 - Social History
 - a. Tobacco use
 - b. Alcohol use
- Duration of Raynaud's phenomenon
- Visual Analog Scale for Pain (VAS Pain)
- Raynaud's Condition Score (RCS)

PROTOCOL TITLE: The Effect of Abobotulinum Toxin A on the Symptoms of Raynaud's Phenomenon, a Double-Blind Randomized Placebo-Controlled Trial

- The Disabilities of the Arm, Shoulder and Hand Score (QuickDASH)
- Number of digital ulcers
- Number of attacks/episodes per week
- Photographs of both hands will be taken during every subject visit and will be stored directly in the password protected HIPAA compliant network drive for clinical research at UCF Health. Though the photos will not contain any identifiers, subjects are potentially identifiable from the photos and thus they will be stored in the password protected HIPAA compliant network drive for clinical research at UCF Health.

10.0 Data and Specimen Banking*

10.1 There will be no data or specimen banking for future use.

11.0 Data Management* and Confidentiality

11.1 The data will be analyzed for significant differences with aid of a statistician. A significance level of 0.05 will be used for statistical hypothesis testing. The results of the data analysis will be graphed for each parameter.

- Categorical variables, such as sex (male and female), age, and comorbidities (e.g., scleroderma) will be reported descriptively, as frequencies and percentages. Outcomes in this study are visual analog scale for pain (VAS Pain), Raynaud's Condition Score (RCS), and the Disabilities of the Arm, Shoulder and Hand Score (QuickDASH), which are continuous variables. In addition, the number of digital ulcers and number of attacks/episodes per week, which are discrete variables, will be measured as outcomes. These continuous and discrete variables will be expressed as mean \pm standard deviation, with standard error of the mean (SEM).
- To assess between group differences, an Independent samples t-tests will be conducted separately for the three time periods: baseline, 1-month, and 3-month. Additionally, a dependent sample t-test will be used to assess within-group differences from 1-month to 3-month, separately for the experimental and control groups. It is possible to use the baseline measurement as a covariate in an analysis of covariance (ANCOVA) and/or in a repeated measures ANOVA. Thus, the researchers will also explore these additional analyses if the sample size permits.
- All tests will be two-sided, and p-values < 0.05 will be considered statistically significant. Statistical analyses will be conducted using SPSS 24.0 (IBM; Chicago, IL).

PROTOCOL TITLE: The Effect of Abobotulinum Toxin A on the Symptoms of Raynaud's Phenomenon, a Double-Blind Randomized Placebo-Controlled Trial

11.2 Utilizing the statistical software G*Power it was determined that 16 patients would be needed to detect a 2-point difference in the RCS among the treatment arms. (G*Power) This assumes a standard deviation of 1.92, power of 0.8, alpha of 0.05, and effect size (d) of 1.04. (Merkel)

11.3 Data will be managed as follows:

- Data will be stored in the secure HIPAA-compliant database called REDCap.
- Unique identifiers will be created using sequential numbers (i.e. 1, 2, 4 etc.).
- No data collection instrument in REDCap will contain identifying information
- The Screening and Enrollment Log, Drug Accountability Log, Eligibility Forms, Demographics Forms, Medical History Forms, Baseline Case Report Forms, Follow Up Case Report Forms, Brief Follow Up Case Report Forms, Adverse Event Forms (see attached documents) will all be stored in the regulatory binder in a locked drawer in a locked room at UCF Health. Only [name] will have access to this locked drawer.
- Photographs will be taken with a UCF Health digital camera. The photographs will then be transferred to a folder on a password protected HIPAA compliant network drive for clinical research at UCF Health. After transfer of photographs to clinical research folder they will be deleted from the camera. Photographs will be labeled with subject ID number and visits number (i.e Subject 01 3-month)
- A subject ID assignment list (see attached document "Subject ID Assignment List") that links the subject name and contact information with their unique identifier will be stored in a separate folder in locked drawer in a locked room at UCF Health. Only [name] will have access to this locked drawer.
- Identifying information such as the "Subject ID Assignment List" will only be accessed by the PI and co-PIs for initial entry. It is possible the identifiable information may be referenced if questionable data are detected during data analysis (e.g.: number out of range, missing data).
- The "Screening and Enrollment Log" and the "Subject ID assignment List" will both be disposed of in a HIPAA-compliant shred bin at the completion of the study.
- Informed consents and HIPAA authorizations will be stored in locked drawer in a locked room at UCF Health and kept for a minimum of six years after the conclusion of the study (per UCF data retention policies.)

PROTOCOL TITLE: The Effect of Abobotulinum Toxin A on the Symptoms of Raynaud's Phenomenon, a Double-Blind Randomized Placebo-Controlled Trial

- Only de-identified data will be used and exported for analysis.
- De-identified data and photographs will be stored for a minimum of five years after the conclusion of the study (per UCF data retention policies).

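### Attacks per week and digital ulcers are compared between two hands of the same patient with independent-samples t-tests, which ignore the pairing and can lose much of the power

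*Combined protocol and SAP*

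**What the plan says.** Section 9.1 randomises hands within a patient by coin flip: "Heads: Right hand – treatment arm; Left hand – control arm", with the reverse for tails. Every patient therefore contributes one toxin hand and one saline hand.

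Section 11.1 names the two counts as outcomes ("the number of digital ulcers and number of attacks/episodes per week, which are discrete variables, will be measured as outcomes") and summarises them in the same way as the scores: "These continuous and discrete variables will be expressed as mean" with SD and SEM. For the comparison of arms, "an Independent samples t-tests will be conducted separately for the three time periods: baseline, 1-month, and 3-month". It gives no separate method for counts.

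The only paired test looks along time within one arm: "a dependent sample t-test will be used to assess within-group differences from 1-month to 3-month, separately for the experimental and control groups". ANCOVA and repeated measures ANOVA are mentioned as exploratory, if the sample size permits. The power statement in section 11.2 covers the RCS only: "16 patients would be needed to detect a 2-point difference in the RCS among the treatment arms".

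Section 12.1 adds an interim comparison at 8 subjects. It applies p < 0.05 to the changes in the same outcomes, both counts included, and names no test.

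**The concern.** The hand-by-hand design lets each patient act as his or her own control. An independent-samples test discards that advantage: its standard error contains the full spread between patients, although that spread largely cancels in the toxin-minus-saline difference. Attack frequency may well vary several-fold between patients, so the cost could be large for this outcome.

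A non-significant result on attacks could then reflect the test rather than the treatment. The fault makes the test too cautious when hands are positively correlated, so it would not by itself explain a significant result. If the same test is used at the interim look, it could also miss a difference there.

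**Working it through.** **The plan's own figure.** d = 2/1.92 = 1.04. A two-sided two-sample t-test at 0.05 with 80% power needs 15.5, so 16 per arm, with power 0.81. The stated 16 therefore reproduces as the per-group size of an independent-groups test on the RCS. Here 16 patients supply 16 hands per arm. No such calculation exists for the counts.

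**Why the planned test is conservative.** Let each arm have variance s² and let ρ be the between-hand correlation. The planned test uses 2s²/16 as the variance of the mean difference; the true value is 2s²(1 − ρ)/16. With no effect, the t statistic therefore has SD of about √(1 − ρ) instead of 1, and it is compared with 2.042 (30 df).

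**Assumed count model (not from the documents).** Poisson counts with mean 7 per week per hand; a patient gamma effect shared by both hands (shape 0.5, 1, 2 or 4, so CV² c = 2, 1, 0.5 or 0.25); and optional independent hand-level gamma variation (shape 4, h = 0.25). Then ρ = 49c / {7 + 49[(1 + c)(1 + h) − 1]}.

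- c = 2, h = 0: ρ = 98/105 = 0.93. √0.067 = 0.26 and 2.042/0.26 = 7.9, so rejection is practically 0%.
- c = 0.25, h = 0.25: ρ = 12.25/34.56 = 0.35. √0.646 = 0.80 and 2.042/0.804 = 2.54, so rejection is about 1.1%.

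Simulation over all eight settings gave 0% to 1.3%, in line with this.

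**Power for a halving of attacks, 16 patients, two-sided 0.05 (simulated).** The four settings with the widest patient variation:

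| Patient shape | Hand-level variation | Independent t (planned) | Paired t | Exact signed-rank |
|---|---|---|---|---|
| 0.5 | no | 6% | 77% | 85% |
| 0.5 | yes | 5% | 35% | 50% |
| 1 | no | 28% | 92% | 93% |
| 1 | yes | 20% | 50% | 60% |

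With milder patient variation, the planned test has 64% (shape 2) and 86% (shape 4) without hand-level variation, and 39% and 58% with it. Signed-rank has 65% to 97% in those four settings and is within about 4 points of the paired t. Over all eight settings the ranges are 5% to 86% (planned), 35% to 97% (paired t) and 50% to 97% (signed-rank).

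**Wider assumptions.** With control means of 5 to 20 per week and CV² of 0.25 to 2, a halving gives 5% to 94% for the planned test against 63% to 99.7% for a paired t.

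**Pairing or skew?** With equally skewed attack counts (mean 10, CV² 1) but no shared patient effect, independent and paired t have about equal power: 37% and 34%. The loss therefore comes mainly from the ignored pairing. Skew adds a smaller part: signed-rank exceeds the paired t by 85 − 77 = 8, 60 − 50 = 10 and 50 − 35 = 15 points in three of the tabulated settings, and by 1 point in the fourth.

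**Ulcers.** Assume gamma shape 0.3 and that toxin abolishes all ulcers. The chance that a saline hand has any ulcer is 1 − (1 + 0.1/0.3)^−0.3 = 8% at mean 0.1, so about 16 × 0.083 = 1.3 patients are informative. At mean 0.5 it is 1 − (1 + 0.5/0.3)^−0.3 = 25.5%, about 4.1 patients. An exact two-sided signed-rank test needs six non-zero differences to reach 0.05 (2 × 0.5⁵ = 0.0625; 2 × 0.5⁶ = 0.031). Simulated power is accordingly about 0.1% at mean 0.1 and 20% at mean 0.5, against about 3% and 42% to 45% for the planned test.

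**The case against.** The strongest objection is that the figures rest on count distributions that the documents do not supply. A reader might infer that the planned test loses almost all its power. The documents do not support that: they give no mean, variance, share of zeros or between-hand correlation, and with modest patient variation the test keeps as much as 86% power for a halving. Near-total loss occurs only when patients differ very widely or the effect is moderate.

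A reader might also blame the discrete, skewed scale. The no-shared-effect comparison shows that this is secondary. The pairing fault applies equally to the RCS and VAS comparisons made under the same sentence, and the preference for signed-rank over a paired t matters only in the more skewed settings.

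It might further be said that the planned test becomes undefined when all between-hand differences are zero. That describes a paired t-test, which the plan does not use between hands. Nor does an exact within-patient test rescue sparse ulcers; in the cases above it does worse than the planned test.

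The plan does provide for a statistician and for exploratory ANCOVA or repeated measures ANOVA. A repeated measures model with hand as a within-patient factor could respect the pairing, but the plan does not specify this, makes it conditional on sample size, and does not let it replace the t-test. The case report forms are attached but not shown, so whether attacks are recorded per hand cannot be checked.

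What stands is that the primary test stated for the counts does not match the design, and that it was weaker than signed-rank in every attack setting examined.

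**Conclusion.** The concern holds in a limited form. For attacks per week, the independent-samples t-test is wrong for a design with both arms in one patient. If hands are positively correlated it is conservative, and for a halving of attacks (assumed mean 7, 16 patients) its power is about 5% to 86% where a signed-rank test has 50% to 97%. The size of the loss within that range cannot be settled from the documents, because it depends on how much patients differ.

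For ulcers the mismatch is the same, but the remedy is weaker: if ulcers are sparse, 16 patients carry too little information for any of these tests, and a non-significant result should not be read as evidence of no effect.

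**What to change.** In section 11.1, replace the independent-samples t-test for attacks per week with an exact Wilcoxon signed-rank test on the within-patient toxin-minus-saline difference, and report the median difference with its confidence interval. Confirm that the case report forms record attacks separately for each hand; without that, no between-hand comparison is possible.

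For ulcers, show the distribution of counts by hand and label any within-patient test as descriptive. A simple conditional binomial test on pooled counts is not a safe substitute: with hand-level overdispersion in simulated attack counts, its type I error rose to about 34%.

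In section 12.1, state whether the comparison at 8 subjects uses the same test.

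The cost is plan wording and a few lines of analysis code. Signed-rank can be slightly weaker than a paired t when counts are sparse: 16% against 21% at an assumed mean of 1 per hand.

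### Section 11.1 plans no estimate or confidence interval for the between-hand difference on which the trial is sized, and the per-arm SEMs it does plan can return only an unpaired interval, not the paired one that fits the split-hand design

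*Combined protocol and SAP*

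**What the plan says.** All references are to the combined protocol and SAP.

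- **Aim of the analysis (11.1):** "The data will be analyzed for significant differences with aid of a statistician".
- **Form of the results (11.1):** VAS Pain, RCS, QuickDASH, digital ulcers and weekly attacks are each given as a mean with "standard deviation, with standard error of the mean (SEM"), and each parameter is graphed. The content of the graphs, including any error bars, is not specified.
- **Between-arm test (11.1):** "an Independent samples t-tests will be conducted separately for the three time periods: baseline, 1-month, and 3-month".
- **Decision rule (11.1):** "All tests will be two-sided, and p-values < 0.05 will be considered statistically significant". The review at 8 subjects in section 12.1 also rests on p < 0.05.
- **Sample size (11.2):** "16 patients would be needed to detect a 2-point difference in the RCS among the treatment arms". "This assumes a standard deviation of 1.92", with "power of 0.8, alpha of 0.05, and effect size (d) of 1.04".
- **Allocation (9.1):** a coin flip decides which hand gets toxin. The other hand of the same patient gets saline, so 16 patients give 16 pairs of hands.

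No section plans the toxin-minus-saline difference as a reported estimate, its SD, or a confidence interval for it. ANCOVA and repeated-measures ANOVA are mentioned in 11.1 only as analyses to explore if the sample size permits.

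**The concern.** The trial is sized on a difference between hands, yet that difference has no planned estimate and no planned measure of precision. A p-value alone does not say whether a non-significant result rules out the 2-point planning difference or is compatible with it. An interval does.

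Per-arm SDs and SEMs are only a partial substitute. The two hands belong to the same patient, so the precision of the contrast depends on the SD of the within-patient difference. That SD depends on the between-hand correlation, which per-arm summaries do not contain. SEM bars drawn for each arm would not show the precision of the paired contrast either.

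Section 2.3 hopes that the data, if positive, could support insurance coverage, and that preliminary findings could justify further studies. Both uses need an effect size with a range around it.

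**Working it through.** **Inputs.** From 11.2: target difference 2 RCS points, SD 1.92, 16 patients, power 0.80, alpha 0.05. From 11.1: two-sided independent-samples t-test. From 9.1: one hand per arm in each patient. The plan does not say whether 1.92 is the SD of a single hand or of the within-patient difference. It is taken here as the per-hand SD. The between-hand correlation r is not in the documents, so it is an assumption and is varied.

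**1. The plan's own figure.** d = 2/1.92 = 1.04. For a two-sided independent t-test (noncentral t), the smallest n with power of at least 0.80 is 16 per arm, with power 0.812. The stated 16 reproduces as 16 hands per arm, that is, 16 patients.

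**2. The interval a reader can rebuild.**
- SEM per arm = 1.92/√16 = 0.48
- SE of the difference, treating the arms as independent = √(0.48² + 0.48²) = 0.679
- Half-width = t(0.975, 30) × 0.679 = 2.042 × 0.679 = 1.39 points

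**3. The interval that fits the design.** SD of the difference = 1.92 × √(2(1 − r)). Half-width = t(0.975, 15) × SD/√16, with t = 2.131. The last column is 1.386 divided by the paired half-width.

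| Assumed r | SD of difference | Paired half-width | Unpaired ÷ paired |
|---|---|---|---|
| 0 | 2.715 | 1.45 | 0.96 |
| 0.3 | 2.272 | 1.21 | 1.14 |
| 0.5 | 1.920 | 1.02 | 1.36 |
| 0.8 | 1.214 | 0.65 | 2.14 |

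If 1.92 is itself the SD of the differences, the half-width is 1.02, as in the r = 0.5 row. At r = 0.3 and 0.5 the nominal 95% unpaired interval actually covers about 98% and 99%.

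**4. When significance alone leaves the question open.** If the observed SD equals 1.92, the unpaired result is non-significant when the observed benefit is below 1.39. Its interval reaches 2 when the benefit is above 2 − 1.39 = 0.61. A benefit between 0.61 and 1.39 is therefore non-significant and still compatible with 2 points. A smaller benefit is non-significant and excludes 2. For the paired interval the window is 0.79 to 1.21 at r = 0.3 and 0.98 to 1.02 at r = 0.5. At r = 0.8 there is no such window, because the half-width is below 1.

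**5. How often this happens if the true difference is 2 points** (simulated trials, with the SD estimated afresh in each). The joint probability is the product of the two columns before it.

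| Analysis | Non-significant | Of those, interval includes 2 | Joint probability |
|---|---|---|---|
| Unpaired (hands independent) | 0.188 | 0.867 | 0.188 × 0.867 = 0.16 |
| Paired, r = 0.3 | 0.092 | 0.80 | 0.092 × 0.80 = 0.07 |
| Paired, r = 0.5 | 0.027 | 0.64 | 0.027 × 0.64 = 0.02 |

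At r = 0.8 the joint probability is essentially zero. For contrast, if the true difference is 0, about 17% of non-significant unpaired trials have an interval reaching 2, against 87% when it is 2. The interval therefore carries information that the significance verdict does not.

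**The case against.** **A reader can rebuild an interval.** This stands. The two arm means and SEMs return the ±1.39 interval that belongs to the planned independent t-test. A reader might infer that a non-significant result cannot be told apart from a missed 2-point effect, or that a significant result gives no range for the benefit. The documents support neither inference. With positively correlated hands the rebuilt interval is generally wider than the paired one, so when it excludes 2 points that conclusion is conservative. What cannot be rebuilt is the paired interval.

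**Section 11.1 does not forbid intervals.** This also stands. A reader might take the listed summaries as the only results to be given, but that is an inference from silence. The difference in means is a simple subtraction, and the named software prints an interval. Even so, nothing commits the trial to reporting one, and with five outcomes and several visits, what is not pre-specified can be reported selectively.

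**The problem case is uncommon under a paired analysis.** This is correct at moderate or high correlation, as step 5 shows. The conditional percentages alone would exaggerate it. The correlation is unknown, however, and the unpaired figure belongs to the test the plan names.

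**This is really the choice of test.** It stands in part, because the missing SD of differences goes with the independent test. But replacing that test with a paired one would still leave 11.1 giving per-arm mean, SD and SEM with a p-value.

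**No section says a null result will be reported as no effect.** This is true, and misreading is a risk rather than a plan. Section 2.3 itself calls the findings preliminary.

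**Conclusion.** The point holds as a reporting gap that should be closed. It does not alter the sample size, which reproduces. No estimate or interval is planned for the between-hand difference, and per-arm SEMs recover only an unpaired interval of about ±1.39 points. That is about 1.1, 1.4 or 2.1 times the paired width at assumed correlations of 0.3, 0.5 or 0.8. If the true difference is 2 points, a non-significant result that remains compatible with 2 has a probability of about 16% unpaired, and 7% or 2% paired at correlations of 0.3 or 0.5.

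These figures rest on 16 complete pairs, 1.92 as the per-hand SD in both arms, approximate normality, and correlations that the documents do not give. If the hands were uncorrelated, the paired interval would be slightly wider (1.45) and pairing would gain nothing in width.

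**What to change.** In section 11.1:

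1. For each outcome recorded separately for each hand, and at each analysed visit, report and graph the mean within-patient toxin-minus-saline difference, its SD and its two-sided 95% confidence interval from the paired analysis. State which outcomes are recorded per hand.
2. Keep per-arm mean and SD as description only.
3. State that an RCS interval containing both 0 and the 2-point planning difference will be described as inconclusive, not as no effect.

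The cost is a few sentences. Sample size, visits and data collection do not change, and the interval is standard output of a paired t-test in the software already named. The between-arm test in 11.1 should be brought into line, so that the p-value and the interval come from the same paired analysis.
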